## 3.2.2 Study Patient Population

In current clinical practice in China, the medications that are used as the first-line treatment of advanced HCC include: VEGFR TKIs, such as sorafenib, lenvatinib, or systemic chemotherapy with oxaliplatin-based single agent or in combination with other agents, such as the FOLFOX4 regimen. Other options include systemic oxaliplatin-based chemotherapy in combination with sorafenib, or arsenious acid chemotherapy, or traditional Chinese medicine. Immune checkpoint inhibitors (for example anti-PD-1 antibody nivolumab) were conditionally approved by the US FDA as the treatment of HCC patients who have progressed after sorafenib treatment. These drugs have not been approved in China for indications of HCC, but they have been widely used in clinical studies or off-label treatments.

Intrahepatic cholangiocarcinoma (ICC) is a rare malignant tumor which arises from the epithelial cells of intrahepatic bile ducts. The incidence of ICC is reported to be only about 10% of primary liver cancers. Unresectable advanced ICCs are usually treated by chemotherapy agents, such as 5-fluorouracil with leucovorin, gemcitabine as a single agent, or gemcitabine plus cisplatin, irinotecan, or capecitabine. For non-resectable cases, the prognosis is very poor and overall mean duration of survival is less than 6 months. Combining lenvatinib (Lenvima) with PD-1 inhibitors showed promising efficacy in patients with advanced intrahepatic cholangiocarcinoma (ICC) who have failed prior treatments with an ORR of 21.4% (3/14) and a median PFS of 5.0 months, according to preliminary data from a single-center study [22] reported at the 2018 Gastrointestinal Cancers Symposium.

In Phase I of the study, besides HCC subjects who progressed after or were intolerant to toxicity of one or more systemic treatments, ICC or mixed HCC-ICC subjects will be also enrolled to explore the initial efficacy of monotherapy or combination therapy in these subjects. These subjects may receive prior first-line or above immune checkpoint inhibitor treatment, VEGFR inhibitors or systemic chemotherapy.

Phase II Part I will only enroll HCC subjects. Study population in the HCC cohort that has failed prior immune checkpoint inhibitors has radiologically confirmed disease progression following anti-PD-1 antibody, anti-PD-L1 antibody or CTLA-4 antibody that have been approved or are in the clinical research & development period. These subjects can only be previously treated with first-line immune checkpoint inhibitors, e.g., PD-1/PD-L1 antibody monotherapy, PD-1/PD-L1 antibody in combination with anti-CTLA-4 antibody or one targeted antiangiogenic drug, or systemic chemotherapy. The molecular targeted antiangiogenic drugs and chemotherapeutic drugs are only allowed to be co-administered. In the cohort that has not previously treated with immune checkpoint inhibitors, subjects have failed or are intolerant to toxicities of targeted antiangiogenic drug and/or systematic chemotherapy without receiving PD-1/PD-L1 antibody or CTLA-4 antibody and other immune checkpoint drugs. Phase II Part 2 will only enroll HCC subjects who have previously treated with immune checkpoint inhibitors to further evaluate the efficacy and safety of the investigational drugs in these subjects.

# 3.2.3 Selection of Efficacy Endpoints

The primary efficacy endpoint of the phase II study was objective response rate (ORR) according to RECIST 1.1. Secondary endpoints included ORR, TTP, PFS, OS, etc. according to irRECIST for immunotherapy, which could provide supportive evidence for clinical benefit.

Current radiologic evaluation criteria that can be applied to HCC include RECIST 1.1 criteria, mRECIST criteria, and irRECIST criteria for immunotherapy. Primary phase III clinical studies of immunotherapy in HCC adopted the RECIST 1.1 criteria (e.g., Checkmate-040 study, study of Atezolizumab in combination with Bevacizumab). The mRECIST criteria have not been fully validated for immunotherapy. Therefore, the ORR assessed according to RECIST 1.1 criteria was used as the primary efficacy endpoint for comparing with other studies. Provided that the characteristics of immunotherapy have been fully considered and a better rationality than RECIST 1.1 in terms of subject management (e.g., discontinuation of investigational drugs after reaching PD), it should be subject to irRECIST in case of investigator-assessed progressive disease and discontinuation of the investigational drugs.

# 4. Study Population

### 4.1 Inclusion criteria

- 1. Subjects who voluntarily sign the informed consent form (ICF);
- 2. Male or female subjects who are aged 18-75 years old;
- 3. Subjects with histologic, cytologic or clinical confirmed diagnosis of advanced HCC (phase I could include intrahepatic cholangiocarcinoma or mixed hepatocellular-cholangiocarcinoma), and are not suitable for surgery or loco-regional therapy or have progressed following surgery and/or loco-regional therapy;
- 4. Subject who has at least one measurable lesion according to RECIST v1.1 criteria.
- 5. Phase I study: subjects who have previously received at least one line of systematic therapy, including immune checkpoint inhibitors, molecular targeted drugs or systematic chemotherapy, alone or in combination, and failed (progression confirmed by imaging) or were intolerant at the discretion of investigator;
  - Phase II Advanced HCC cohort with subjects who have previously received immune checkpoint inhibitor treatment: subjects who have failed (progression confirmed by imaging) prior first-line immune checkpoint inhibitor treatment, including anti-PD-1 antibody/anti-PD-L1 antibody and / or anti-CTLA-4 antibody, and/or molecular targeted therapy or systematic chemotherapy (monotherapy or in combination);
  - Phase II Advanced HCC cohort with subjects who have not previously received immune checkpoint inhibitor treatment in Phase II study: subjects who have failed (progression confirmed by imaging) or were intolerant to (at the discretion of investigator) previous molecular targeted therapy or systematic chemotherapy, without receiving immune checkpoint inhibitor treatment (including anti-PD-1 antibody, anti-PD-L1 antibody, anti-CTLA-4 antibody, and bispecific antibodies including the above targets).
- 6. Previous anti-tumor therapy must be completed no less than 2 weeks prior to the study treatment and all adverse events related to previous treatment must have recovered to CTCAE Grade ≤1; if subjects who have received prior immune checkpoint inhibitors have immune-related endocrinopathy, it should be controlled with hormone replacement therapy.
- 7. Phase I: cirrhotic status of Child-Pugh Class A; Phase II: cirrhotic status of Child-Pugh Class A or B with a score of 7;
- 8. Eastern Cooperative Oncology Group (ECOG) Performance Status score of 0 or 1.
- 9. Subjects with life expectancy  $\geq$  12 weeks;
- 10. Subjects with chronic HBV infection must have HBV-DNA <500 IU/ml, and have received at least 14 days of anti-HBV treatment (e.g. entecavir, tenofovir) prior to the initiation of study treatment and are willing to receive antiviral treatment throughout the study; Antiviral therapy is not required for patients with HCV infection and the elevation of their liver enzymes must not exceed the level of CTCAE Grade 1;
- 11. Adequate organ function as outlined below:
  - (1) Blood system function (subjects must have not received blood transfusion or stimulating growth factors within 14 days prior to screening test): neutrophil count  $\geq 1.5 \times 10^9 / L$ , platelet count  $\geq 75 \times 10^9 / L$ , hemoglobin  $\geq 90 \text{ g/L}$ ;
  - (2) Liver and kidney function (no albumin transfusion within 14 days prior to

screening test): serum total bilirubin  $\leq 2.5 \times \text{ULN}$ , serum albumin  $\geq 29 \text{ g/L}$ , ALT and AST  $\leq 5 \times \text{ULN}$ ; serum creatinine  $\leq 1.5 \times \text{ULN}$  or eGFR (Cockcroft-Gault formula)  $\geq 60 \text{ ml/min}$ ;

- (3) Coagulation function: international normalized ratio (INR) $\leq$ 2.3 or prothrombin time (PT) of  $\leq$  6 seconds above control;
- (4) Left ventricular ejection fraction (LVEF) ≥50% by two-dimensional echocardiography.
- 12. Female subjects (except for females who have underwent surgical sterilization and those have been menopausal for more than one year) who are of childbearing potential are required to adopt a medically acceptable contraceptive measure (such as intrauterine device, contraceptive pill or condom) throughout the study and up to 120 days after the last dose of investigational products; females must have negative serum or urine HCG tests within 7 days prior to enrollment; female subjects must not be breastfeeding; male subjects whose partners are of childbearing potential should use effective contraceptive methods throughout the study and up to 120 days after the last dose of investigational product.
- 13. Subjects who are willing to provide oncological tissues (if applicable) for biomarker test.

### 4.2 Exclusion criteria

- 1. Subjects who have known fibrolamellar carcinoma of liver for phase I and subjects who have fibrolamellar carcinoma, mixed HCC- cholangiocarcinoma or cholangiocarcinoma for phase II;
- 2. Subjects with brain metastasis or leptomeningeal metastasis confirmed by brain MRI during screening period;
- 3. Subjects with a diagnosis of other malignant tumors within 5 years prior to first administration, except for skin basal cell carcinoma, skin squamous cell carcinoma and/or in situ cancer following radical resection;
- 4. Subjects who had liver or other sites loco-regional treatment (including transcatheter arterial chemoembolization (TACE), transcatheter arterial embolization (TAE), hepatic artery infusion (HAI), local radiotherapy, radioembolization, radiofrequency ablation, cryoablation or percutaneous ethanol injection), or who had major surgery of liver or other sites within 4 weeks prior to first administration, or had minor surgical procedures (such as simple excision, tooth extraction, etc.) within one week prior to first administration, or had received palliative radiotherapy for bone metastasis within 2 weeks and radiotherapy-related toxicity  $\geq$  CTCAE Grade 2.
- 5. Subjects who have moderate or severe ascites (detected by B-ultrasound or CT), or require therapeutic abdominal paracentesis or drainage;
- 6. Subjects with a history of hepatic encephalopathy;
- 7. Subjects with a history of unhealed wounds or ulcers or bone fractures within 3 months prior to study treatment
- 8. Subjects who plan to have or had allogenic organ or bone marrow transplantation
- 9. Subjects who are at increased risk of bleeding or have history of thrombosis:
  - (1) Clinically significant bleeding within 3 months prior to screening or clear bleeding

tendency;

- (2) Gastrointestinal hemorrhage within 6 months prior to screening or clear tendency of gastrointestinal hemorrhage;
- (3) Arterial/venous thromboembolic events within 6 months prior to screening, such as cerebrovascular accident (including transient ischemic attack), pulmonary embolism, etc.;
- (4) Require anticoagulation therapy with an agent such as warfarin or heparin;
- (5) Require chronic anti-platelet therapy (such as aspirin≥100 mg/day, clopidogrel, etc.);
- 10. Subjects who have clinically significant cardiovascular diseases:
  - (1) NYHA (New York Heart Association) stage 3 and 4 congestive heart failure;
  - (2) Unstable angina pectoris or newly diagnosed angina pectoris or myocardial infarction within 12 months prior to screening;
  - (3) Arrhythmias requiring medications other than  $\beta$ -blockers;
  - (4) Valvular heart disease of  $\geq$  CTCAE Grade 2;
  - (5) Hypertension inadequately controlled by drugs (systolic pressure >150 mmHg or diastolic pressure >90 mmHg);
- 11. Subjects who have history of symptomatic pulmonary fibrosis, interstitial pneumonitis, pneumoconiosis, radiation pneumonitis, drug-related pneumonitis, or severe impairment of pulmonary function, or other suspicious pulmonary diseases that may interfere with drug-related pulmonary toxicity detection and treatment
- 12. Subjects who have suffered active bacterial or fungal infections requiring systematic treatment within 7 days prior to screening; or active tuberculosis;
- 13. Subjects with active co-infection of Hepatitis B and C, confirmed by positive HBV surface antigen or HBV DNA and HCV RNA;
- 14. Subjects who have any active, known or suspected autoimmune disease
- 15. Subjects with a condition requiring systematic treatment with corticosteroids (>10 mg/day prednisone or equivalent) or other immunosuppressive drugs within 14 days before administration of the investigational drug. In the absence of active autoimmune diseases, inhalation or topical use of steroids (>10 mg/day prednisone or equivalent) is allowed;
- 16. Other laboratory abnormalities:
  - (1) Hyponatremia, hypokalemia or hypophosphatemia that have occurred before the first administration, and failed to restore to normal level after electrolyte supplementation therapy;
  - (2) Confirmed diagnosis of thyroid dysfunction, which cannot be maintained within normal range following thyroid hormone replacement therapy;
  - (3) Positive Human immunodeficiency virus (HIV) test;
- 17. QTc interval >480 ms on two consecutive ECGs;
- 18. Female subjects during pregnancy or lactation; female subjects of childbearing potential or male subjects who are not willing to use contraception or contraceptive measures

- during the study;
- 19. Subjects who have previously received two lines and above tumor immune checkpiont inhibitor treatment, mainly including anti-PD-1, anti-PD-L1 and anti-CTLA-4 antibodies, etc, or bispecific antibodies including the above targets, or received anti-LAG-3 antibody; whether subjects who have previously received other tumor immunotherapy can be enrolled should be determined by the sponsor;
- 20. Known or suspected history of severe allergy to investigational drugs;
- 21. Subjects who have received live attenuated vaccines or any investigational drugs that have not been marketed in China within 4 weeks prior to first administration;
- 22. If subjects who have previously used immune checkpoint inhibitors (such as anti-PD-1, anti-PD-L1, anti-CTLA-4 antibodies) have the following adverse events related to immune checkpoints, they will be not suitable for inclusion regardless of recovered or not:
  - a)  $\geq$  Grade 3 eye-related adverse events
  - b) Grade 4 abnormal liver function
  - c)  $\geq$  Grade 3 neurotoxicity
  - d) ≥ Grade 3 colitis
  - e)  $\geqslant$  Grade 3 renal toxicity
  - f)  $\geqslant$  Grade 3 pneumonitis
- 23. Subjects who are not suitable for inclusion as judged by the investigators.

## 4.3 Discontinuation of Subjects from Treatment

### 4.3.1 End of Treatment

Subjects may discontinue treatment at any time during the study. End of Treatment Visit (EOT) should be performed within 7 days of decision date to discontinue treatment.

Study drug shall be permanently discontinued in any of the following cases:

- Adverse Event
  - Occurrence of any CTCAE (V5.0) grade 3 or 4 treatment-related adverse event, which fails to recover to CTCAE Grade 1 or below within 4 weeks (28 days) (unless the investigator believes that the subject may continue to benefit from treatment and the continuation requires the permission from sponsor's medical monitor);
  - CTCAE Grade 3 or 4 treatment-related adverse event recurs in combination treatment group despite dose reduction of brivanib alaninate;
  - Myocardial ischemia and/or infarction;
  - Evidence for abnormal cardiac valve function ≥ CTCAE Grade 2;
  - LVEF decrease by > 10% from baseline-ECHO and LVEF < 45%;
  - QTc > 500 milliseconds on 3 consecutive ECGs performed during the same visit and in the absence of possible causes other than study therapy;

- Torsade de pointes or sustained ventricular tachycardia;
- Hemorrhage ≥ CTCAE Grade 3;
- Gastrointestinal perforation;
- Arterial thromboembolic event;
- Venous thromboembolic events of CTCAE Grade 3 or 4;
- Hypertensive crisis;
- Immune-related adverse events of grade 4.
- Disease progression according to irRECIST criteria
- Risk to the subject as judged by the investigator and/or sponsor
- Critical violation to the protocol as judged by the investigator and/or sponsor
- Subject's decision
- Pregnancy
- Death
- Completion of protocol-defined therapy (MGD013 monotherapy)

If the reason for treatment discontinuation is not disease progression, death, withdrawal of informed consent or loss to follow-up, radiologic tumor assessments will still be performed at protocol-specified intervals until disease progression by irRECIST or the starting of subsequent antitumor therapy (Phase II).

### 4.3.2 End of Study

Patients who are no longer on treatment but are still followed on the study can be terminated from the study for the following reasons:

- Death
- Lost to follow up
- Withdrawn of consent
- The study is terminated

# 5. Study Treatment

### **5.1 Investigational Products**

Investigational products of this study are shown in the table below:

Table 2. Investigational Products for Clinical Study

Name of	Brivanib alaninate Tablets	MGD013 injection
investigational drug		
Appearance	Light yellow to yellow biconvex oblong film-coated tablets	Sterile injection
Strength	200mg	300 mg/15 mL
Administration route	Oral administration	Intravenous infusion

Brivanib alaninate is given orally at the dose according to subject's dose group once daily at a fixed time, and can be taken with or without meals; If subject vomits after a dose or misses a dose, additional dose should not be taken on the same day.

In the dose escalation period, the starting dose of MGD013 was 120 mg IV on day 1 of each cycle, once every two weeks; the dose sequentially escalated to 240 mg, 400 mg and 600 mg IV, Q2W; MGD013 may be administered at a level or frequency beyond the above examples according to safety data obtained from the study and other studies.

Before intravenous infusion, MGD013 at each dose level must be diluted with 0.9% sodium chloride injection, USP (normal saline) 100 mL or 250 mL of infusion bags. The final concentration of MGD013 for infusion after dilution with normal saline must be between 0.12 mg/mL and 6.4 mg/mL. It is administered for 60 - 75 minutes. A 0.2 µm sterile and pyrogen-free inline filter made of polyether sulfone (PES) with a low protein-binding rate must be adopted for IV infusion since there may be visible semi-transparent protein particles in the solution.

### 5.2 Infusion preparation

### 5.2.1 General Guidelines and Precautions

MGD013 should not be administered as an IV push or bolus. All doses of MGD013 will be diluted in normal saline and administered as an IV infusion with a commercially available infusion instructions, see Pharmacy Manual for details. The final concentration of MGD013 for infusion after dilution with normal saline must be between 0.12 mg/mL and 6.4 mg/mL. It is administered for 60 - 75 minutes. All infusion instructions must be calibrated in accordance with the institutional standards, policies, and procedures to ensure consistent, accurate delivery of MGD013.

Infusion or allergic reactions may occur with the infusion of mAbs and other protein-based therapeutics. Precautions for anaphylaxis should be observed during MGD013 administration. Supportive measures may include, but are not limited to, epinephrine, antihistamines, corticosteroids, IV fluids, vasopressors, oxygen, bronchodilators, diphenhydramine, and acetaminophen. Please refer to Section 8.4.1 for specific guidelines regarding the management of infusion reactions. Supportive care measures consistent with optimal patient care will be provided throughout the study according to institutional standards.

### 5.2.2 Study Drug Preparation and Administration

Visually inspect parenteral drug products for particulate matter and discoloration prior to administration. Return the vial if the solution is cloudy, there is pronounced discoloration (solution may have pale-yellow or pale brown color), or there is foreign particulate matter. Instructions on the preparation of the study drugs for IV infusion are detailed in the Pharmacy Manual.

Do not mix the study drug with, or administer as an infusion with, other medicinal products. The study drugs do not contain preservatives. Once diluted in normal saline, the dose solution is stable up to 4 hours at room temperature or 24 hours stored refrigerated at 2° to 8°C with minimal exposure to light. If the dose solution is stored at 2° to 8°C, it should be removed from the refrigerator at least 30-60 minutes prior to administration to allow the dose solution to reach room temperature. Precautions should be taken to minimize the time between dose preparation and IV infusion.

### 5.3 Concomitant medication

Any medication the subject takes other than the study treatment, including prescribed, non-prescribed, Chinese herbal medicine and dietary supplements, should be considered as concomitant medication.

All previous and concomitant medications must be recorded in the eCRF. It must include: generic name, route of administration, start and completion time, dosage and indications related to each concomitant medication. Any changes to the product of concomitant medication should also be recorded in the eCRF. At Screening, subjects will be asked what medications they have taken during the last 30 days. At each subsequent study visit, subjects will be asked what concomitant medications they are currently taking.

### **5.3.1 Prohibited Medications**

- Other anti-tumor therapies, such as chemotherapy, immunotherapy, therapeutic radiation, experimental anticancer drugs or loco-regional therapy, are not allowed while the subject is using the investigational drug; palliative radiotherapy is allowed for non-target lesions that are present prior to enrollment with uncontrolled pain that cannot be relieved by local or systemic analgesics, provided that there is no disease progression.
- Corticosteroids should be limited because MGD013 has a mechanism of action dependent upon the engagement of T lymphocytes. Chronic use of corticosteroids > 10 mg/d of prednisone or equivalent are prohibited other than for the management of drugrelated adverse reactions. Corticosteroids for topical (e.g., ophthalmic, inhaled, or nasal) administration are allowed.
- The concomitant use of rifampin (and its analogues);
- Hypericum perforatum or traditional Chinese medicines with indications for the treatment of liver cancer (including but not limited to Xiaoaiping, Kanglaite, Cinobufotalin, Elemene and Delisheng Injection) is not allowed.
- Vaccination with live vaccines is not allowed within 28 days prior to the first dose and during the study.
- Prophylactic use of stimulating factors (eg, granulocyte colony-stimulating factor) is not allowed during the first cycle of therapy.
- Anticoagulation therapy such as warfarin or heparin is not allowed when the subjects are administrated with the investigational products.

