## **Definition of evaluable subject**

An evaluable subject is defined as a subject who received  $\geq 75\%$  of pre-specified total dose of MGD013 and brivanib alaninate (combination treatment cohort) within the first two cycles (28 days) and has completed primary safety evaluation, **or** experiences DLT at any time within 28 days.

A cycle lasts for two weeks (14 days) in the study, and the first two cycles are the DLT evaluation period. Provided that 3 or 6 evaluable subjects in one dose group have completed the first two cycle evaluation and the dose escalation criteria is met, subsequent dose cohort is open to enroll. There will be no intra-subject dose escalations. Unevaluable subjects in Phase I will be replaced until at least 3 evaluable subjects are enrolled in each dose group. Approximately  $30 \sim 43$  evaluable subjects will be enrolled. The total number of subjects will depend upon the number of dose levels.

Subjects will continue treatment until disease progression, death or the occurrence of intolerable toxicity, whichever comes first. MGD013 will be used for at most 48 cycles. Subjects receiving combination therapy can continue using brivanib alaninate if there is still no disease progression after discontinuing MGD013.

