### 3.1.2 Dose Escalation Rules

During dose escalation study of monotherapy, the starting dose of MGD013 will be 120 mg Q2W with single subject in this dose cohort. If no  $\geq$  Grade 2 drug-related adverse events occur during the DLT observation period within 28 days after the first administration, the dose may escalate sequentially. The subsequent dose groups will adopt traditional 3+3 dose escalation scheme. If adverse events of CTCAE Grade 2 or above related to the drug are observed in the subject of the starting dose group, the study will convert to traditional 3+3 scheme for all dose groups, and at least another 2 evaluable subjects will be enrolled in starting dose group.

The study will not proceed with the 3+3 design in case of the following drug-related adverse events, that is, only one subject enrolled in the starting dose group:

- Grade 2 anemia
- Grade 2 endocrinopathy that is well controlled with hormone replacement therapy
- Grade 2 nausea, vomiting, dyspepsia, diarrhea or constipation that resolve to grade

[figure not shown]
1 or baseline within 48 hours after medical intervention

- Grade 2 fatigue that resolves to grade 1 within 4 days
- Grade 2 fever or flu-like syndrome that resolves to grade 1 or baseline within 24 hours after medical intervention
- Grade 2 infection that resolves to grade 1 or baseline within 72 hours after medical intervention
- Grade 2 lymphocytes or neutrophils decreased
- Grade 2 amylase or lipase increased that resolves to Grade 1 or baseline within 72 hours
- Grade 2 electrolyte disturbance that resolves to Grade 1 or baseline within 72 hours after medical intervention
- Grade 2 cancer pain
- Grade 2 headache, cough and shortness of breath that resolve to grade 1 or baseline within 24 hours after medical intervention

Except the starting dose group of monotherapy, other dose groups and combination therapy groups will adopt traditional 3+3 dose escalation scheme. Dose escalation follows the following principles:

- If no dose-limiting toxicity (DLT) is observed in a cohort of at least 3 evaluable subjects then dose escalation may occur;
- If one subject experiences a DLT in a group of 3 evaluable subjects, then the cohort will be expanded to include 3 evaluable subjects. If only one DLT is observed in the complete cohort of 6 evaluable subjects, then dose escalation may occur;

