- If 2 or more subjects experience a DLT in a group of up to 6 subjects, dose will be deescalated to prior dose level and more subjects may be enrolled until there are 6 evaluable subjects in this dose group.
- If 2 or more subjects in the lowest-dose group experience a DLT during MGD013 monotherapy, the study will be terminated;
- If 2 or more subjects experience DLT in the starting dose group of the combination therapy (MGD013 400mg q2w+brivanib 400mg qd), the combination dose level escalation will be terminated.
- The dose of MGD013 and brivanib alaninate will not exceed 600mg Q2W and 800mg QD (monotherapy MTD).
- RP2D dose groups of the monotherapy and combination therapy should at least enroll 6 evaluable subjects.

The 3+3 dose escalation scheme is shown below.

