### 3.1.3 Dose-Limiting Toxicity (DLT)

DLT was defined as the following adverse events (AEs) occurring within 4 weeks (the first 2 cycles, 28 days) after the investigational drugs which is at least possibly related to the study drugs:

- Hematologic Adverse Events:
  - Grade 4 neutropenia lasting  $\geq 5$  days;
  - Febrile neutropenia lasting > 48 hours or any febrile neutropenia with hemodynamic instability or an objective evidence of infection;
  - Grade 4 thrombocytopenia or Grade 3 thrombocytopenia with obvious hemorrhage;
  - ≥ Grade 3 haemolysis
- Non-hematological adverse events:
  - ≥ Grade 3 gastrointestinal reactions and electrolyte abnormal, e.g., nausea, vomiting, diarrhea constipation and abdominal pain that persist (more than 72 hours) despite an adequate medical intervention;
  - Sustained /repeated ≥3 grade hypertension which recurred despite sufficient medical interventions (BP ≥ 150/100 mmHg means 2 measurements taken at least 24 hours (h) apart ≥ 150/100 mmHg, taken after the subject had been seated/lying quietly for 10 minutes. At least 1 week was taken to evaluate subject's response to a change in antihypertensive medication (initiation or increase in antihypertensive medication). Once stabilized on antihypertensives, for 1 week, a subsequent episode of ≥150/100 was to be considered the "second event").
  - Other ≥ Grade 3 non-hematological toxicity, excluding:
    - Alopecia;
    - Grade 3 infusion-related reaction or cytokine release syndrome (CRS) that resolves after medical intervention within 12 hours

- Grade 3 fever that lasts < 72 hours and is not associated with hemodynamic compromise
- Grade 3 fatigue that lasts < 72 hours
- Grade 3 skin toxicity that resolves to ≤ Grade 2 within 14 days of initiation of oral corticosteroids
- Grade 3 endocrinopathy that is well controlled with hormone replacement therapy
- Grade 3 amylase or lipase increased without clinical or radiographic evidence of pancreatitis
- Grade 3 tumor inflammatory reaction (local inflammatory response at tumor or metastasis focuses attributed to an antitumor effect of drug, e.g., swelling, pain, fever) that resolves to ≤ Grade 2 within 7 days
- ➤ Grade 2 ocular pain or vision decreased that does not resolve to Grade 1 by topical therapy within 14 days, or that requires systemic treatment;
- ➤ Hepatic dose-limiting toxicity:
  - For subjects with  $\leq$  grade 2 baseline transaminases increased ( $\leq$  3 × ULN):

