## **Definition of maximum tolerated dose (MTD)**

[figure not shown]
It is defined as the maximum dose at which <33% subjects suffer from DLTs; if 2 or more DLTs occur in a certain dose group, this dose is considered as intolerable, its prior dose level is defined as the maximum tolerated dose (MTD). There must be at least 6 evaluable subjects in the MTD dose group.

In Phase I dose escalation period, the **Safety Review Committee** (SRC) will decide whether to escalate to the next dose level or discontinue the escalation after reviewing the data from each dose group.

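### The Phase I bar on prophylactic growth factors stops at Day 14, half-way through the 28-day DLT window

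*Combined protocol and SAP*

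**What the plan says.** Among the prohibited medications, Section 5.3.1 has one rule on growth factors during treatment: "Prophylactic use of stimulating factors (eg, granulocyte colony-stimulating factor) is not allowed during the first cycle of therapy".

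Section 3.1.1, in its definition of an evaluable subject, fixes the time scale: "A cycle lasts for two weeks (14 days) in the study, and the first two cycles are the DLT evaluation period". A subject is evaluable after receiving at least 75% of the planned dose "within the first two cycles (28 days) and has completed primary safety evaluation", or after a DLT at any time in the 28 days. Growth-factor use plays no part in that definition. The same text adds: "Unevaluable subjects in Phase I will be replaced until at least 3 evaluable subjects are enrolled in each dose group".

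Section 3.1.3 lists four haematologic DLT criteria, two of which concern neutrophils. One is Grade 4 neutropenia of at least 5 days. The other is "Febrile neutropenia lasting > 48 hours or any febrile neutropenia with hemodynamic instability or an objective evidence of infection".

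Section 3.1.2 turns DLT counts into dose decisions, and the SRC "will decide whether to escalate to the next dose level or discontinue the escalation after reviewing the data from each dose group".

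**The concern.** A bar on prophylaxis in a dose-finding phase keeps supportive medication from hiding the toxicity being counted. Here it lapses half-way through the counting period. A subject could receive G-CSF around the Day 15 infusion, avoid a neutropenia event or have it shortened below the DLT threshold, and enter the 3+3 count as evaluable with no DLT.

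DLT-free status over 28 days drives escalation, the MTD and both RP2Ds. For the neutropenia criteria the gap works in one direction only: fewer DLTs counted. The protocol also has a rule of the same kind with the right span. Section 8.4.3 bars Phase I dose reduction throughout the DLT observation period.

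**Working it through.** **Span of the rule against span of the window**

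- DLT window: 2 cycles x 14 days = 28 days. This reproduces the figure in Sections 3.1.1 and 3.1.3.
- Growth-factor bar: 1 cycle x 14 days = Days 1-14.
- Not covered: 28 - 14 = 14 days (Days 15-28), and 14/28 = 50% of the window.

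**Does another section close Days 15-28?**

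- Inclusion criterion 11 (Section 4.1) bars growth factors in the 14 days before the screening test, which is before treatment.
- Section 5.3.3 allows best supportive care by institutional standards, with an open-ended list, and does not exclude growth factors.
- The evaluable-subject definition is silent.

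None of these closes it.

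**Do the open days include study drug?**

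- Planned MGD013 in the window: two equal infusions, Days 1 and 15, with no intra-subject escalation.
- 75% of 2 infusions = 1.5 infusions. Day 1 supplies at most 1.0.
- A DLT-free evaluable subject must therefore receive at least 1.5 - 1.0 = 0.5 of the Day 15 infusion.

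So every DLT-free evaluable subject has new MGD013 exposure in the uncovered half. For G-CSF, 2 of the 4 haematologic DLT criteria are open to masking.

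**What one prevented DLT would do under Section 3.1.2**

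The rules are: 0/3 escalate; 1/3 expand to six; at six, "If only one DLT is observed in the complete cohort of 6 evaluable subjects, then dose escalation may occur"; and "If 2 or more subjects experience a DLT in a group of up to 6 subjects, dose will be deescalated to prior dose level". Because the design is sequential, it matters where the prevented DLT fell.

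| Count without masking | How it arises | Count with one DLT prevented | Does the decision change? |
|---|---|---|---|
| 1/3 | first three | 0/3 | Yes: escalate without expanding |
| 2/3 | first three | 1/3 | Yes: expand instead of de-escalate |
| 3/3 | first three | 2/3 | No |
| 1/6 | 1/3, then 0/3 | 0/3 | No: the level is cleared either way, with fewer subjects |
| 2/6 | 1/3, then 1/3 | 0/3 or 1/6 | Yes: escalate instead of de-escalate |
| 3/6 | 1/3, then 2/3 | 0/3 if the prevented DLT was in the first three; otherwise 2/6 | Yes in the first case, no in the second |

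De-escalation is not the consequence at every level. Under Section 3.1.2, two or more DLTs end the study at the lowest monotherapy dose, and end combination escalation at the starting combination dose.

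The table shows what one prevented event could do. It does not say how often that would happen, and the documents give no neutropenia DLT rate or rate of prophylactic use.

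**The case against.** The strongest reply is that nothing in the documents suggests the gap would be used.

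- **Neutropenia is not expected.** Section 1.1.3.2 names no neutropenia among MGD013 events in at least 10% of 36 patients, nor among the Grade 3 related events. It reports no related Grade 4-5 events at doses up to 1,200 mg, twice this trial's 600 mg ceiling. Section 1.1.4.2.3 names none for brivanib among the events above its reporting thresholds. This largely stands. The common-event lists are cut at thresholds, though, and describe the drugs separately, while this trial escalates the combination.
- **Stopping rules remove the likeliest users.** Section 8.4.3 stops both drugs in the combination group for related Grade 3-4 events until recovery. Its last paragraph stops MGD013 for drug-related Grade 3 events until recovery and permanently for Grade 4. That paragraph sits in the discussion of immune-related events, so its reach to monotherapy is arguable. A subject who misses the Day 15 infusion has at most 50% of planned MGD013, and so is either a DLT or not evaluable and replaced. This also stands. What remains is a subject with milder neutropenia, or one who recovers in time to be dosed in Cycle 2.
- **Use would be visible.** Section 5.3 has concomitant drugs recorded with dates and indication, Table 1 schedules haematology on Days 8, 15, 22 and 29, and the SRC reviews each dose group. The SRC could notice, but no rule tells it to look.
- **Silence is not permission.** The protocol nowhere endorses prophylaxis on Days 15-28. But a prohibition limited to Cycle 1 naturally reads as not applying in Cycle 2, and sites could differ.

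A reader might go further and infer that the MTD or RP2D will be biased, or that half the window unprotected means a large share of DLTs lost. The documents do not support either. The 50% counts days of wording, and G-CSF acts only on the neutropenia criteria. Any calculated rise in the chance of escalation would rest on an assumed share of masked DLTs that no section supplies.

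**Conclusion.** The mismatch is confirmed as a stated rule with the wrong span. It leaves 14 of 28 DLT days, one of two MGD013 infusions and two of four haematologic DLT criteria without the protection given in Cycle 1. Its direction is anti-conservative. Its practical size cannot be calculated from the documents and is probably small, given the events listed for each drug and the stopping rules.

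This is a minor correction. Confidence is high for the textual mismatch and does not extend to any effect on the selected dose. The conclusion assumes that the Cycle 1 limit means what it says, and that the subject meets the 75% dose rule, completes the safety evaluation and has no other DLT.

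**What to change.** In Section 5.3.1, for Phase I, replace the first-cycle limit with *the DLT observation period (first two cycles, 28 days)*, the period Section 8.4.3 already uses for dose reduction. Add one sentence: *Any prophylactic growth factor given in this period is listed for the SRC before its escalation decision.* The uncovered span falls from 14 days to 28 - 28 = 0. Phase II needs no change.

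G-CSF to treat an actual event should stay allowed. It could still shorten Grade 4 neutropenia to under 5 days, and this change does not address that.

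I would not add a rule replacing DLT-free subjects who received prophylaxis. It would remove subjects according to outcome and could tilt the observed DLT rate upward. The listing gives the SRC the information without that side effect.

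The cost is one phrase and one sentence. Section 10.6 requires ethics approval before use, so it belongs in the next amendment and should apply to Phase I cohorts opened after it. It adds no subjects, visits or tests.
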